4.1.7.1 Visit windows

As subjects do not always adhere to the terms and conditions defined in the study protocol, visit windows will be used to assign each clinical assessment to a scheduled visit (for data that will be summarised by visit, as shown in [Table 9](#), [Table 10](#), and [Table 11](#)).

To apply the visit windows, note the following rules for defining the start and end of each study period:

- The ST period starts from Day 1 (start date of IP) and ends on the start date of the Week 26 visit or early discontinuation from the study, whichever is earlier. For subjects who did not enter the LT period, there is no cut-off date.
- For subjects entering the LT period, the LT period starts from the day after the end of the ST period and ends on the date of Week 56 visit or early discontinuation from the study, whichever is earlier.
- The Randomised Withdrawal period starts from the date of first intake of third randomisation treatment (i.e., IP issued on the Week 32 or Week 40 visit) and ends on the date of Week 56 visit or early discontinuation from the study, whichever is earlier.
- The post-study period starts from the day after the end of the LT period and ends on the date of Week 104 visit or date of lost to follow-up, whichever is earlier.

For subjects who entered the LT period but skipped the Week 26 visit, then the event date from the Continuation Long Term Follow up CRF will be used (if available). For subjects who entered the post-study period but skipped the Week 56 visit, then the latest visit date during the ST+LT period will be used to extrapolate the estimated Week 56 date (target day 395).

Prior to slotting the data must be restricted to the cut-offs defined for each variable and period as per [Table 8](#). Slotting must be repeated for each type of analysis applicable to a variable (primary and each sensitivity analysis).

Visit windows for post-baseline (after Day 1) assessments that will be slotted for the ST period are shown in [Table 9](#). Visit windows for assessments that will be slotted for the LT and randomised withdrawal period and the post-study (Week 104) visit are shown in [Table 10](#) and [Table 11](#).

Table 9 Visit windows for ST period assessments

Visit	Target Day	Day Range by Type of Assessment		
		Vital Signs	Safety laboratory panel, FPG, HbA1c, PK/PD ^a , Urinary glucose, Height, Weight	Growth and maturation markers, Tanner staging, ECG, Fasting lipid panel
Week 6	43	2 to 64	2 to 64	
Week 12	85	65 to 92	65 to 113	
Week 14	99	93 to 120		
Week 20	141	121 to 162	114 to 162	
Week 26	183	163 to Week 26/ED (whichever is earlier)	163 to Week 26/ED (whichever is earlier)	2 to Week 26/ED (whichever is earlier)

ED = Early discontinuation from the study.

^a PK/PD assessments include plasma samples for analysis of dapagliflozin, saxagliptin, 5-OH-saxagliptin, FPG and DPP-4 activity.

Table 10 Visit windows for LT period and post-study (Week 104) assessments

Visit	Target Day (LT Day ^a)	Day Range by Type of Assessment	
		Vital signs, Safety laboratory panel, FPG, HbA1c, Height, Weight	Growth and maturation markers, Tanner staging, ECG, Fasting lipid panel
Week 32	225 (43)	LTSTDT to 252 / RWSTDT [only applicable for subjects going through the third randomisation] (whichever is earlier)	
Week 40	281 (99)	253 / RWSTDT +1 [only applicable for subjects going through the third randomisation] (whichever is earlier) to 322	
Week 52	365 (183)	323 to Week 56/ED (whichever is earlier)	LTSTDT to Week 56/ED (whichever is earlier)
Week 104	728	Growth and maturation markers, Tanner staging, Height, Weight, BMI Week 56 + 1 day to Week 104 / date of last contact (if earlier than Week 104)	

ED = Early discontinuation from the study. LTSTDT = LT start date (i.e., day following the last day of the ST period). RWSTDT = randomised withdrawal period start date (i.e., date of first IP dose received in randomised withdrawal period).

^a LT day is the target day counting from the start of the LT period (LTSTDT). Target day is based on counting from Day 1 (date of first IP dose in the study).

Table 11 Visit windows for randomised withdrawal period assessments

Visit	Target Day	Date Range by Type of Assessment	
		Vital signs, Safety laboratory panel, FPG, HbA1c, Height, Weight	Growth and maturation markers, Tanner staging, ECG, Fasting lipid panel
Withdrawal Baseline		The closest available value on or before RWSTDT	
Week 40	281	RWSTDT +1 day to 322 (for subjects who were third randomised at Week 32 only)	
Week 52	365	RWSTDT + 1 day (for subjects who were third randomised at Week 40) or 323 (for subjects who were third randomised at Week 32) to Week 56 visit/ED (whichever is earlier)	RWSTDT to Week 56 visit/ED (whichever is earlier)

ED = Early study discontinuation. RWSTDT = randomised withdrawal period start date (i.e., date of first IP dose received in randomised withdrawal period).

For laboratory and non-laboratory parameters, if a subject has more than one measurement included within a window, the assessment closest to the target day will be used. In case of ties between observations located on different sides of the target day, the earlier assessment will be used. In case of ties located on the same side of the target day (i.e. more than one value for the same day but different time), the value with the earlier entry date/time will be used. For observations with the same date and time, including missing times and including potential baseline values, an average will be taken if the two or more values with the same date and time.

In addition, for the efficacy FPG analyses as there are multiple time points collected at each visit, then the record with the earliest time on the day selected using the above definition will be used for each visit in the analysis. If there are multiple values collected with the same time, then an average will be taken. If there are multiple values collected on the same day where one of the records only has the date available, then the records with the date/time present are selected over the records with only date present. Only FPG assessments documented with the subject in a fasting state will be summarised and listed.

For the shift tables for nominal ECG parameter of normal/abnormal the following rules apply. If more than one ECG measurement is performed within a specified time window, an abnormal ECG value will be chosen over a normal ECG value. If two or more abnormal or two or more normal ECG values are within the same time window, the one closest to the target date will be used.

Data collected during unscheduled visits will also be slotted.

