Exploratory analyses for the monotherapy period will include only subjects who are on background medication with metformin and have HbA1c measurement < 7.5% at Week 26 or Week 32. Analyses will be performed using the HbA1c value at the withdrawal baseline. The reference time point to be used as 'withdrawal baseline' will be the closest time point on or before the third randomization. The period starting from this baseline to Week 52 will be referred to as the 'randomized withdrawal period'.

For subjects recruited into the study prior to the study site implementation of the third protocol amendment, participation in the third randomization (with possible withdrawal of background medication with metformin) will be at the subject's discretion.

Adverse events and serious adverse events (SAEs) will be assessed during a Week 56 phone visit.

In case a visit is delayed for any reason, subsequent visits should be scheduled such that an interval of at least 12 weeks is maintained between the:

- Week 14 visit and the Week 26 visit.
- Third randomization (for subjects undergoing third randomization; occurring at the Week 32 or the Week 40 visit) and the Week 52 visit.

If more than 12 weeks elapse between the HbA1c collection at Week 26 and the third randomization at Week 32, or the HbA1c collection at Week 32 and the third randomization at Week 40, the subject should not go through this randomization, as the HbA1c value would no longer be reliable to ascertain eligibility for the third randomization. Short- and long-term period study visits can be delayed by a maximum of 11 months in total. If the duration of IP administration is longer than 52 (+1) weeks, the safety follow-up period should be shortened such that the complete study duration does not exceed 104 weeks (+7 days). A window period of -28 days to +7 days from the original scheduled date will be allowed for the Week-104 visit.

Subjects who discontinue study drug before the end of the study treatment period will enter a non-treatment, follow-up phase, in which subjects will follow their visit schedules with modified assessments until study completion. Subjects will attend a post-study visit at Week 104, for assessment of measures of growth and maturity. This visit should be completed without delay (at 104 weeks (+7 days) from Day 1, regardless of whether any other study visits were delayed.

All subjects with HbA1c > 8.0% at and after Week 26 will be rescued.

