| Second randomization | | | | | X | | | | | | |
| Dispense Study Drug | X | | X | | X | X | X* | * No study drug dispensed during ETD or Rescue Visit. Rescued subjects will continue with their current assigned IP regimen. | | | |
| Study Drug Compliance Review | | | X | | X | X | X | | | | |
| General | | | | | | | | | | | |
| Provide diet and exercise counseling | X | X* | X | X | X | X | X | *Assessed by Phone | | | |
| Dispense meter supplies | X | | X | X | | X | X | | | | |
| Review daily diary of finger-stick glucose values | X | X* | X | X | X | X | X | *Assessed by Phone | | | |
| Provide logs / instructions | X | | X | X | | X | X | | | | |
| Assess Rescue | | | X | X | X | X | X | | | | |

 $^{^{}a}$ Visits may be scheduled \pm 7 days (of original schedule) to allow flexibility of scheduling. Week 12 and Week 14 visits should be scheduled at least 7 days apart. The visit window for the Rescue Visit assessments starts at the site's receipt of the HbA1c alert or FPG confirmation.

b Phone assessments

In case the Week 14 visit is delayed, subsequent visits should be delayed to maintain an interval of at least 12 weeks between the Week-14 and Week-26 visits. Short- and long-term period study visits can be delayed by a maximum of 11 months in total.. If the duration of IP administration is longer than 52 (+1) weeks, the safety follow-up period should be shortened such that the complete study duration does not exceed 104 weeks (+7 days).

d Samples will be drawn at the times shown in Table 5.5-1 Sampling Schedule

Table 5.1-3: Long-term Procedural Outline (CV181375 [D1680C00019])

| | | Wk | | | Wk 52 / | | Quarterly | Wk 104 | |
|---|-------------------------|-----------|-------------------------|-------------------------|--|----------------------|-----------------------------------|---------------------|--------------------|
| Procedure | Wk 32 ^{a,c} | 36 a,b | Wk 40 ^{a,c} | Wk 46 ^{a,b} | early discontinuation of IP)/Rescue ^a | Wk 56 ^{a,c} | between Wk 56 and Wk 104 | Post-study Visit | Notes |
| Eligibility Assessments | | | | | | | | | |
| Review concomitant medications/procedures | X | X* | X | X* | X | | | | *Assessed by Phone |
| Safety Assessments | | | | | | | | | |
| Physical Examination | | | | | X | | | | |
| Targeted Physical Examination | X | | X | | | | | | |
| Tanner Staging (Investigator determined/Self-reported) | | | | | X | | | X | Appendix 3 |
| Vital Signs | X | | X | | X | | | | |
| Height | X | | X | | X | | | X | |

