Revised Protocol 05	24-Sep-2020	
The protocol was revised to specify that visits should be delayed to maintain an interval of at least 12 weeks between the Week 14 and Week 26 visits and between the third randomisation visit (for subjects undergoing third randomisation) and the Week 52 visit in case the Week 14 or third randomisation visit is delayed. This change was instituted because HbA1c is derived from the average of the blood glucose fluctuation in the preceding 3 months and therefore, approximately 12 weeks of exposure to a new dose is needed to demonstrate efficacy.
 
Short- and long-term period study visits can be delayed by a maximum of 11 months in total. If the duration of investigational product administration is longer than 52 (+1) weeks, the safety follow-up period should be shortened such that the complete study duration does not exceed 104 weeks. The Week 104 visit should not be delayed.
 
If more than 12 weeks elapse between the HbA1c collection at Week 26 and the third randomisation at Week 32, or the HbA1c collection at Week 32 and the third randomisation at Week 40, the subject should not go through this randomisation as the HbA1c value would no longer be reliable to ascertain eligibility for the third randomisation.
 
Other updates include guidance on changes needed to the clinical conduct due to the coronavirus disease 2019 (COVID-19) pandemic (e.g., sending the investigational product directly to subjects' homes, home visits by study site personnel/vendor, allowing off-site monitoring visits); updates to the text for consistency with the latest AstraZeneca template; and minor clarifications.

Revised Protocol 06 07-Feb-2022 The following revisions were made to the protocol:
To allow for flexibility in scheduling, the window period for Week 104 post-dose visit was modified from “± 7 days” to “-28 days to + 7 days” from the original scheduled date.

Based on discussions with FDA, the primary objective was modified to assess the effect of all doses and regimens combined for each drug versus placebo.

In line with this, the primary and secondary objectives were reordered and updated. The reordering was done to make overall analysis (all doses for each treatment) as the primary objective.

The primary objective was updated as follows:

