4.1.1 Definitions

Baseline

Unless stated otherwise, for each subject, baseline value of a parameter (e.g., efficacy laboratory parameter, safety laboratory test, ECG or physical measurement endpoint) is defined as the last assessment on or prior to the date of the first dose of the double-blind study medication in the ST treatment period (Day 1).

If there are multiple assessments with the same date and time, the average value will be used as baseline.

For subjects belonging to the Randomised Withdrawal Subjects Data Set, the withdrawal baseline value for a given parameter is defined as the closest available value on or before the day of first dose in the Randomised Withdrawal period.

Change from baseline

Change from baseline to any Week t in the analysis period (i.e., ST treatment period and ST+LT treatment period) is defined as follows:

$C_{Week\ t} = M_{Week\ t} - M_{baseline}$,
where:

- $C_{Week\ t}$ is the change from baseline at Week t ,
- $M_{Week\ t}$ is the measurement at Week t ,
- $M_{baseline}$ is the measurement at baseline.

The “Week t ” to which a measurement belongs is determined using the conventions described in [Table 8](#) (Section 4.1.6).

Last observation carried forward (LOCF)

A post-baseline missing value will be imputed by the last available non-missing post-baseline or post-withdrawal baseline (as applicable) value. If the first scheduled post-baseline or post-withdrawal baseline value is missing, no imputation will be done.

Day 1 is the date of first dose of study drug in the ST period.

Study day is defined relative to the date of first dose (Day 1) received in ST treatment period, and is calculated as:

- If assessment date is before the date of first dose: assessment date - date of first dose in the ST period (Day 1).
- If assessment date is on or after the date of first dose: assessment date - date of first dose in the ST period (Day 1) + 1.

Treatment response to HbA1c

A treatment responder at Week t is a subject with HbA1c $< 7\%$ at Week t (irrespective of baseline value). HbA1c response at Week t will be derived by dichotomising HbA1c values at Week t (binary variable, set to 1 if HbA1c $< 7\%$ at Week t and 0 if HbA1c $\geq 7\%$ at Week t). Where specified, missing HbA1c responses at Week t will be derived from imputed continuous values of HbA1c for Week t .

Rescue medication initiation

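### A Week 20 sample taken on Day 163 or later can replace the true Week 26 sample as the Week 26 HbA1c or FPG endpoint

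*SAP*

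**What the plan says.** SAP 4.1.1 anchors the day count: "Study day is defined relative to the date of first dose (Day 1) received in ST treatment period". In SAP 4.1.7.1, Table 9 gives HbA1c and FPG a Week 20 window of Day 114 to 162 (target 141). The Week 26 window (target 183) opens on Day 163 and closes at the actual Week 26 visit or early study discontinuation.

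Within a window, "if a subject has more than one measurement included within a window, the assessment closest to the target day will be used". The tie rule is: "In case of ties between observations located on different sides of the target day, the earlier assessment will be used". For efficacy FPG, the same rule chooses the day, and the earliest record on that day is then used. The LT period begins the day after the Week 26 visit. Nothing in the section favours the sample taken at the nominal Week 26 visit, and nothing moves Day 183 when visits slip.

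The protocol allows visits to slip. Section 3.1 says that if a visit is delayed for any reason, "subsequent visits should be scheduled such that an interval of at least 12 weeks is maintained" between Week 14 and Week 26. The footnote to Table 5.1-2 says that after a late Week 14, "subsequent visits should be delayed to maintain an interval of at least 12 weeks between the Week-14 and Week-26 visits", and adds: "Short- and long-term period study visits can be delayed by a maximum of 11 months in total". Protocol 1.1 and 3.1 also state that 26 weeks of treatment means treatment up to the Week 26 visit.

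**The concern.** The two documents use different clocks. The protocol lets the Week 26 visit move so that enough time passes after the Week 14 dose assignment. The SAP keeps Day 183 fixed from first dose. Once Weeks 20 and 26 have both slipped far enough, the late Week 20 sample lies nearer to Day 183 than the sample from the visit that was postponed. The SAP then uses Week 20 and drops Week 26.

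The amendment histories give the reason for the interval: "approximately 12 weeks of exposure to a new dose is needed to demonstrate efficacy". That reason is about HbA1c. The comparisons most exposed are therefore high dose versus low dose on HbA1c among subjects re-randomised at Week 14 (items 9 and 11 in SAP 4.5.1). The primary endpoint and Week 26 FPG pass through the same slotting.

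The SAP did adapt other windows. Table 10 ties the Week 32 and Week 40 ranges to the start of treatment after the third randomisation. The Week 26 target was not adapted.

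**Working it through.** **Inputs.** From SAP Table 9: target days 99 (Week 14), 141 (Week 20) and 183 (Week 26); Week 26 window from Day 163 to the Week 26 visit. From SAP 4.1.7.1: nearest to Day 183 wins, ties to the earlier. From Protocol Table 5.1-2: routine tolerance of ±7 days.

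**Reproducing the plan's figures.** Target day = 7 × week + 1, which gives 99, 141 and 183. The Week 20/26 boundary is the midpoint, (141 + 183)/2 = 162, so the Week 26 window opens on Day 163, as printed.

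**General condition.** Let Week 20 be sampled on Day a and Week 26 on Day b, with b > a.
- If a ≤ 162, Week 20 is outside the window and Week 26 is used.
- If 163 ≤ a < 183, Week 20 wins when 183 − a ≤ b − 183, that is, when b ≥ 366 − a. Equality counts because ties go to the earlier sample.
- If a ≥ 183, Week 20 always wins, because b is further away.

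| Week 20 day a (days late) | Week 20 is used once Week 26 is on or after | Week 26 days late |
|---|---|---|
| 162 or earlier (21 or fewer) | never | – |
| 163 (22) | Day 203 | 20 |
| 171 (30) | Day 195 | 12 |
| 177 (36) | Day 189 | 6 |
| 183 or later (42 or more) | always | any |

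**Equal delay d.** Put a = 141 + d and b = 183 + d. The distance condition gives 183 + d ≥ 366 − 141 − d, so d ≥ 21. The window condition 141 + d ≥ 163 gives d ≥ 22, which is the binding one.
- d = 21: Week 20 on Day 162 is outside the window; Week 26 on Day 204 is used.
- d = 22: Day 163 (20 days off target) beats Day 205 (22 days off).
- d = 42: Day 183 (0 off) beats Day 225 (42 off).

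**Time from Week 14 to the sample used.**
- Delay starting at or before Week 14, nominal spacing kept: (141 + d) − (99 + d) = 42 days. The Week 26 sample would give (183 + d) − (99 + d) = 84 days.
- Week 14 on Day 99, delay starting at Week 20: 163 − 99 = 64 days at d = 22; 171 − 99 = 72 at d = 30; 183 − 99 = 84 at d = 42.
- Only Week 26 late: Week 20 stays on Day 141, so selection is correct.

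**Within ±7 days.** The latest Week 20 is Day 148, 15 days short of the window, so none of the 15 × 15 = 225 combinations of the two visits goes wrong.

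**The displaced sample.** The Week 32 window opens the day after the Week 26 visit, so a Week 26 sample that loses the comparison is not picked up at another analysis visit.

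**The case against.** Nearest-to-target windowing is common, prespecified and independent of treatment arm. It keeps time since first dose close to 26 weeks: with a 42-day delay it takes a sample at exactly Day 183 rather than one at Day 225. The protocol's sentence on 26 weeks of treatment interprets duration and is not a record-selection rule. The trigger is also narrow: Week 20 must be at least 15 days beyond its +7-day limit and Week 26 must be late enough as well. No text requires Week 20 to move by the same number of days as Week 26.

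Most of this stands as a limit on the point. It does not rescue the rule. The protocol ties 26 weeks to the visit and has that visit delayed to secure 12 weeks after Week 14, yet the SAP can discard the very sample for which the visit was delayed.

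Three stronger readings are tempting, and the documents do not support them.
- A reader might infer that the primary result is biased. That analysis pools all doses, and a displaced sample is still at least 162 days (about 23 weeks) after first dose. The 12-week reason concerns a new dose.
- A reader might infer that every affected subject has only six weeks on the assigned dose. That holds only for delays starting at or before Week 14 with nominal spacing kept. With later-starting delays the shortfall shrinks, and at 42 days it is gone.
- A reader might take the 11-month allowance as evidence of long delays before Week 26. It is a ceiling for short- and long-term visits together, and says nothing about how often it is used.

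**Conclusion.** The mechanism is certain on the text: with Week 20 on Day 163 or later and Week 26 on Day 366 − a or later, the endpoint labelled Week 26 comes from the Week 20 visit. The effect on the estimates cannot be sized, because the documents give neither the number of such subjects nor a basis for a direction of bias.

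The clearest harm is to items 9 and 11, where 42 days after the Week 14 assignment may stand in for 84. Item 9 is formally tested only if the primary test and eight secondary tests succeed, and item 11 only if the primary and ten do. The stated 12-week reason appears in the amendment histories; the current protocol text keeps the interval without repeating the reason. The rule should be changed, because the correction is small and the same slotting feeds the primary endpoint, Week 26 FPG and the responder endpoints.

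**What to change.** For the Week 26 efficacy endpoints, use the sample from the nominal Week 26 visit whenever it exists, and apply the Table 9 day windows only when it is missing. With an equal 22-day delay starting at Week 14, this uses Day 205 (84 days after a Week 14 visit on Day 121) instead of Day 163 (42 days after). Report by arm how many subjects' selected record differs between the two rules. If data are already unblinded, keep the current rule and present the nominal-visit version as a sensitivity analysis.

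The cost is one derivation rule and its wording. The nominal visit name is already held (SAP 4.1.7 sorts listings by it), so no new data are needed. There are two downsides. In affected subjects the late Week 20 sample then serves no analysis visit, as the Week 26 sample does now, so one observed value is still set aside. Time from first dose to the endpoint will also vary more. The same precedence could be applied at Week 52, but this is optional: those endpoints are exploratory and no calculation was made for them.
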